2 STUDY OBJECTIVES

2.1 Primary Objectives

2.1.1 To estimate the effect of supplementation with genistein on the time to neutrophil count recovery following myelosuppressive chemotherapy

2.2 Secondary Objectives

2.2.1 To estimate the effect of supplementation with genistein on short-term side effects of myelosuppressive chemotherapy

2.2.2 To estimate levels of the serum markers of inflammation during cycles of chemotherapy given in conjunction with genistein supplementation versus placebo

DRAFT

3 SUBJECT ELIGIBILITY

Eligibility must be reviewed and confirmed by a study investigator prior to subject enrollment.

3.1 Inclusion Criteria

- [1] Newly diagnosed solid tumor or lymphoma with histological verification
- [2] Age 1 - 21 years at time of diagnosis
- [3] Karnofsky/Lanksy performance score of ≥ 50
- [4] Able to tolerate enteral medication administration
- [5] Planned chemotherapeutic regimen for a patient must meet **all** of the following criteria:
 - a. A known myelosuppressive regimen which includes at least two of the following agents: actinomycin, carboplatin, cisplatin, cyclophosphamide, daunorubicin, doxorubicin, etoposide, ifosfamide, topotecan
 - b. At least four consecutive cycles
 - c. Cycle length is either 14 or 21 days
 - d. Regimen **must either alternate myelosuppressive chemotherapeutic agents in an X-Y-X-Y format**, such that the same chemotherapy is given every other cycle (e.g. vincristine/doxorubicin/cyclophosphamide | ifosfamide/etoposide), **or repeat the same chemotherapeutic agents each cycle in an X-X-X-X format** (e.g. repeated cycles of cisplatin/etoposide/bleomycin). Courses eligible for this trial may occur at any time during treatment provided that they are consecutive and follow the one of the described patterns. Non-myelosuppressive anti-neoplastic treatments will not be considered for the purposes of determining eligibility. Questions regarding whether or not a patient's chemotherapy plan meets inclusion criteria will be decided by the Study Chair.
- [6] Informed consent or parental permission and assent obtained prior to trial-related activities ([Section 4.3](#))
- [7] Able and willing to comply with all study related procedures
- [8] Women of childbearing potential must agree to use adequate contraception prior to study entry and for the duration of study participation. Should a woman become pregnant or suspect she is pregnant while participating in this study, she should inform her treating physician immediately.

3.2 Exclusion Criteria

- [1] Known allergy to soy or any soy-based food or supplement
- [2] Unable or unwilling to discontinue consuming prohibited soy-based food or supplements while participating in this study ([Section 4.8.1](#))
- [3] Pre-existing neutropenia or neutrophil qualitative or quantitative disorder ([Section 6.3](#))
- [4] Pre-existing cytopenia or bone marrow failure syndrome
- [5] History of gastric or duodenal ulcers or hyperacidity syndromes
- [6] History of Human Immunodeficiency Virus (HIV)
- [7] Has an active infection requiring systemic therapy
- [8] Planned treatment does not include myelosuppressive chemotherapy
- [9] Enrolled on a therapeutic or supportive care clinical trial within the last 30 days
- [10] Current acute or chronic leukemia diagnosis
- [11] Requires medication dosing via an enteral feeding tube that terminates in the duodenum or jejunum. (Enteral feeding tubes that terminate in the stomach are acceptable for study medication delivery.)
- [12] Pregnant or breastfeeding woman
- [13] Incarceration
- [14] Secondary malignancy, i.e. the cancer for which the patient is presently or will be receiving treatment may not be a malignancy related to prior cancer therapy
- [15] Any condition which might be worsened by estrogen, such as breast cancer, uterine cancer, ovarian cancer, endometriosis or uterine fibroids
- [16] Any condition, in the investigator's opinion, that would compromise patient safety or study outcomes
- [17] Anyone who, in the investigator's discretion, would be unwilling or unable to comply with study procedures

3.3 Enrollment Exceptions

An enrollment exception is the sponsor's prospective approval for the enrollment of a single research subject that fails to meet current approved protocol inclusion criteria or satisfies protocol exclusion criteria. Enrollment exceptions will not be granted on this study.

4 TREATMENT PLAN

4.1 Subject Status Definitions

Enrolled: All subjects who sign an informed consent will be considered enrolled on the study.

Screen Failure: A subject who is withdrawn or discontinues from the study prior to receiving any protocol therapy (genistein or placebo) is considered a screen fail. Screen failures do not count toward accrual and will be replaced.

On Study: An enrolled subject is considered on-study/registered when a site investigator has determined that the subject has met all of the inclusion and none of the exclusion criteria, and the Study Chair, Study Research Coordinator, or designee has confirmed the eligibility. The on study date is the date that eligibility is confirmed at UVa.

Randomized: A subject that has been assigned to an arm is considered randomized.

On Treatment: A subject is considered on-treatment on the date that the protocol therapy (genistein/placebo) is initiated (i.e. Cycle 1 Day 1).

Off Treatment: The off-treatment date is the date that the subject, for any reason, is no longer receiving protocol therapy (genistein or placebo). It begins the day after the last dose of study supplement.

On Follow-up: A subject is considered on follow-up on the date that the protocol therapy is completed or discontinued for any reason listed in [Section 4.9](#). The on follow-up date is described below.

- Protocol therapy completed per protocol: date after Cycle 4 Last Day, same as off-treatment date
- Early discontinuation of protocol therapy: same as off-treatment date
- Screen failure: date determined to be ineligible

Off Follow-up: A subject is considered off follow-up when he or she has completed the follow-up period or the last date of follow-up if withdrawn during this period

Off-Study: A subject is considered off-study if he or she is removed from the study for any of the reasons listed in [Section 4.10](#) or if he or she has completed follow-up. It begins the date that the subject's participation in protocol activities has ended and typically coincides with the off-follow-up date.

- Follow-up period completed per protocol: date of six months post-treatment review
- Screen failure: date determined to be ineligible
- Withdrawn from study: date withdrawn

4.2 Recruitment

Recruitment will be managed by each site's local Institutional Review Board (IRB) with oversight by the Sponsor. See Procedure Manual for additional information.

4.3 Informed Consent

In obtaining and documenting informed consent, the investigator must comply with the applicable regulatory requirement(s), and must adhere to all ICH E6 principles, Good Clinical Practice (GCP), and ethical principles that have their origin in the Declaration of Helsinki.

Before recruitment and enrollment onto this study, the subject and/or his or her parent(s)/guardian(s) will be given a full explanation of the study and will be given the opportunity to review the consent form. Each consent form must include all the relevant elements currently required by the FDA Regulations and local or state regulations. Once this essential information has been provided to the subject/parent(s)/guardian(s) and the investigator is assured that the subject/parent(s)/guardian(s) understand(s) the implications of participating in the study, the adult subject will be asked to give consent or parent(s)/guardian(s) to provide permission to participate in the study by signing an IRB-approved consent form.

Prior to a subject's participation in the trial, the written informed consent form must be signed and personally dated by the subject/parent(s)/guardian(s) and by the person who conducted the informed consent discussion.

Oral assent will be obtained from minor subjects ≥ 7 years old, unless more stringent requirements are imposed by a site's IRB. In addition, consent must be requested from subjects who become pregnant during the course of the study for the purposes of following the subject and fetus. The format of consent from a pregnant subject will be determined by the site's IRB policies. The Sponsor will provide oversight of all consent/permission/assent activities (see Protocol Section 3.1 criterion #6, Procedure Manual).

4.4 Registration

Subjects who have consented to the study must be registered in OnCore (an online clinical trials management system) in accordance with the UVa Cancer Center OnCore standard operating procedures, which can be found on the [UVa OnCore Resources webpage](#) (see the OnCore Help tab). General guidelines are provided in the Procedure Manual for reference, but registration must follow the OnCore SOP in case of any discrepancy.

Subject eligibility must be confirmed by the site PI and the eligibility packet must include at a minimum the informed consent and eligibility worksheet. All sites will then submit an

eligibility packet for each eligible subject to the Study Manager for review (Procedure Manual).

4.5 Randomization or Arm Assignment

Following completion of subject registration as described in [Section 4.4](#), the subject will be randomized by the Study Manager at UVa using custom randomization software developed at UVa. The software incorporates the randomization scheme generated by the Biostatistician and assigns the subject to one of the two arms. The arm assignment will only be available to unblinded site personnel for the purposes of dispensing protocol therapy, the Core Investigational Pharmacist, Study Manager, and Biostatistician. See the Procedure Manual for additional information.

Randomization must occur within the 2 days prior to the anticipated Cycle 1 Day 1.

4.6 Unblinding

Subjects and the study team, with the exception of the site Investigational Pharmacist or designee, will be blinded to the randomization assignment. In the event that an Investigator believes that for the safety of the subject the blind must be broken, the Investigator may contact the site Investigational Pharmacist or designee to unblind the subject. When a subject unblinding occurs, the Study Chair, Biostatistician, and Study Manager must be notified in writing within 5 business days, and the reason must be fully documented and recorded on a Case Report Form (CRF).

Unblinded subjects must immediately discontinue protocol therapy ([Section 4.9](#)) and will be considered to be in Follow-up.

4.7 Dosage and Administration

4.7.1 Chemotherapeutic Regimen

The chemotherapeutic regimen must meet the inclusion criteria described in [Section 3.1](#). Administration of anti-neoplastic therapy must follow standard clinical practices, including dosing delays and dose modifications to anti-neoplastic therapy. See [Section 4.7.3](#) for information pertaining to treatment delays.

If the pre-treatment audiogram for subjects scheduled to receive platinum-based chemotherapy is indicative of severe hearing loss, the chemotherapeutic dose should be adjusted according to standard clinical practices. Any change(s) to the anticipated cancer treatment regimen must be captured in OnCore.

4.7.2 Genistein/Placebo Supplementation

For the purposes of this study, the duration of treatment cycles will coincide exactly with chemotherapy cycles. "Cycle 1" here refers to the first chemotherapy cycle during which the subject receives genistein or placebo, though this may not be the actual first cycle of the subject's chemotherapeutic treatment.

Subjects will receive 30 mg genistein (Arm A) or placebo (Arm B) daily throughout Cycles 1 & 2, beginning on the first day of the first cycle of chemotherapy coinciding with this study (Cycle 1 Day 1) and ending two days prior to the predicted start date of Cycle 3. Following a 2-day washout, subjects will then receive placebo (Arm A) or 30 mg genistein (Arm B) throughout chemotherapy Cycles 3 & 4, beginning on the first day of Cycle 3 and ending on the last day of Cycle 4. **The treatment schedule is summarized on Roadmaps, located in the Procedure Manual appendices.** For the purposes of this clinical trial, “study supplement” will refer to both genistein and placebo.

The study supplement will be delivered orally by the subject or a parent, and a diary will be kept to document dose administration. For doses given at home, subjects and parents will be instructed to bring unused pills to study visits. For children who are unable to swallow tablets, instructions for crushing and administering will be given to the families (Procedure Manual). Tablets may be crushed and delivered via feeding tube only if subjects are unable to take the medication orally and the feeding tube terminates in the stomach. Delivery to the duodenum or jejunum may alter genistein pharmacokinetics.

Subjects will record study treatments on a daily Pill Diary to indicate number of doses and time of dosing (Procedure Manual). If a subject misses a dose by less than 12 hours, he or she must be instructed to take the missed dose. If a subject misses a dose by more than 12 hours, he or she must be instructed to skip the missed dose and continue with regular dosing schedule. However, he or she must redose if vomiting occurs within the first 20 minutes after study supplement ingestion. Redosing may occur only once per 24 hour period.

4.7.3 Treatment Delays

A treatment delay is when scheduled therapy is postponed, typically due to toxicity or scheduling difficulties. This trial contains no scheduled treatment delays. Subjects must continue to take the genistein/placebo supplementation if an anti-neoplastic treatment delay occurs, except in the following circumstance: If the anti-neoplastic treatment delay occurs after the subject has stopped taking the study supplement because of the scheduled washout between Cycles 2 and 3, then genistein/placebo must be held until Cycle 3, Day 1.

See [Section 6.3](#) for additional information on study assessments during treatment delays.

4.7.4 Dose Modifications

Dose modifications for AEs which are at least possibly treatment-related are must follow Table 1. Dose modifications for reasons other than treatment-related AEs are not permitted. See [Section 9](#) for information pertaining to the severity and attribution of AEs.

Table 1. Dose Modifications by Adverse Event Grade for Initial Presentation

Grade	Action
Grade 0 - 1	No change
Grade 2	Reduce dose of the study supplement to 50% (½ tablet)
Grade 3 - 4	Suspend treatment

Return to prior dose after three consecutive days of resolution/baseline grade, or the beginning of Cycle 3. If the rechallenge results in toxicity possibly/probably/definitely attributed to the study supplement, reduce the supplement to 50% of full dose (grade 2) or discontinue treatment (grades 3 – 4) until the start of Cycle 3 or the end of Cycle 4, whichever comes first.

The study supplement must be started at the full dose at the beginning of Cycle 3, regardless of any dose modifications during Cycles 1 and 2. This is because the agent used during Cycles 1 and 2 differs from that which is used during Cycles 3 and 4.

Table 2. Dose Modifications by Adverse Event Grade Following Rechallenge

Grade	Action
Grade 0 - 1	No change
Grade 2	Reduce study supplement dose to 50% (½ tablet) until the start of Cycle 3 or the end of Cycle 4, whichever comes first
Grade 3 - 4	Suspend treatment until the start of Cycle 3 or the end of Cycle 4, whichever comes first

If treatment-related AEs are concurrent, modify the dose based upon the highest grade demonstrated. Rechallenge with the previous dose only after all treatment-related AEs have resolved or returned to baseline.

Pill splitting may be necessary and will not alter genistein pharmacokinetics. The Procedure Manual contains further information about pill splitting.

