4.9 Discontinuation of Protocol Therapy

Subjects will receive genistein or placebo for four 14- or 21-day cycles of chemotherapy, depending upon chemotherapeutic regimen, or until any of the following occur:

- Development of a secondary condition which, in the investigator’s opinion, would compromise patient safety or study results
- A female subject becomes pregnant
- Non-compliance with study procedures or protocol therapy (missing more than 20% of prescribed doses of genistein/placebo) since the first dose of study supplement treatment
- Consumption of prohibited soy-based products more than once during the Treatment Phase ([Section 4.8.1](#))
- Unacceptable AE(s). Subjects who experience [National Cancer Institute \(NCI\) Common Terminology Criteria for Adverse Events \(CTCAE\) Version 4](#) grade 3 or higher AE that is possibly, probably, or definitely related to the genistein/placebo during Cycle 3 or 4
- Chemotherapy regimen is altered such that it no longer meets Inclusion Criterion #5 ([Section 3.1](#))
- Subject’s treatment assignment is unblinded ([Section 4.6](#))
- Subject decides to discontinue protocol therapy

If a subject discontinues protocol therapy for any of the above reasons, the subject will be considered “Off-treatment” and the subject will be “On Follow-Up”. Subjects removed

from protocol therapy for (an) unacceptable AE(s) will be followed until resolution or stabilization of the AE.

Should a pregnant subject consent, the subject will also be followed to determine the outcome of her pregnancy (including any premature termination of the pregnancy). Generally, follow-up will be requested by the Sponsor no longer than 8 weeks following the delivery or termination date.

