9.2 Required Reporting

9.2.1 UVa Cancer Center DSMC Reporting Requirements

All AEs must be reported into UVa Cancer Center OnCore database within the time frame specified below. All timeframes are expressed in (calendar) days from the first point at which any member of the study team learned of the event.

For the purposes of reporting AEs for DSMC review, expectedness is defined in relationship to treatment with the investigational agent. I.e. Is the AE in question expected when undergoing genistein treatment? See Sections [5.1.7](#) and [5.2.4](#) for the expected AE. AEs meeting the thresholds below require additional reporting in OnCore beyond the routine data capture associated with a reporting period.

Target AEs do not need to be reported apart from routine data capture unless they meet the criteria below. Progressions, recurrences, and secondary malignancies must be reported within 30 days of the end of the reporting period during which they occurred, or the next quarterly deadline, whichever comes last. See the Procedure Manual for additional information pertaining to data capture.

Table 5. DSMC reporting requirements for AEs that occur during Cycles 1 – 4

Attribution to Study Supplement	Grades 1 & 2		Grade 3		Grade 4	Grade 5
	Expected & Unexpected		Expected & Unexpected		Unexpected	Unexpected
	Target AEs ¹	All other:	Target AEs ¹	All other:		
Unrelated	OnCore: 30 days/quarterly ³	Not required	OnCore: 30 days/quarterly ³	Not required	OnCore: 30 days/quarterly ³	See SAE
Unlikely				OnCore: 30 days from end of Cycle		
Possible				OnCore: 15 days from end of Cycle		
Probable						
Definite						
SAE ⁴	OnCore: (24-hrs), 7 days ²					

¹ Target AEs: Neutrophil count decreased, infection (any), mucositis oral, febrile neutropenia, fever, tinnitus & hearing impaired (subjects on platinum-based chemotherapy only), peripheral

motor neuropathy (subjects on vincristine only).
² Enter into Cancer Center database within 24 hours and submit supporting documentation within 7 days.
³ Data to be entered within 30 days of the end of the reporting period or the next quarterly deadline, whichever comes last. Deadlines are Jan. 31, Apr. 31, July 31, and Oct. 31.
⁴ Any AE that is an SAE must be reported using the SAE timeline regardless of grade or attribution.

Less stringent reporting is required during the follow-up period.

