Table 6. DSMC reporting requirements for AEs that occur after the subject’s last cycle taking the study supplement until 6 months post-treatment (i.e. follow-up)

Attribution to Study Supplement	Grades 1 & 2	Grade 3	Grade 4	Grade 5
	Expected & Unexpected	Expected & Unexpected	Unexpected	Unexpected
Unrelated Unlikely	Not required	Not required	OnCore: 30 days/quarterly ²	See SAE
Possible Probable Definite		OnCore: 30 days from end of Reporting Period ³	OnCore: 15 days from end of Reporting Period ³	
SAE ⁴	OnCore: (24-hrs), 7 days ¹			

¹ Enter into Cancer Center database within 24 hours and submit supporting documentation within 7 days.
² Data to be entered within 30 days of the end of the reporting period or the next quarterly deadline, whichever comes last. Deadlines are Jan. 31, Apr. 31, July 31, and Oct. 31.
³ Reporting is not required if AE onset is > 30 days after the last dose of study supplement
⁴ Any AE that is an SAE must be reported using the SAE timeline regardless of grade or attribution.

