9.2.3.2 Additional Reporting Requirements for Affiliate Sites

In addition to reporting in OnCore, all SAEs must be reported by facsimile within 24 hours of the event to the Sponsor (UVa) as outlined in the Procedure Manual. Any SAEs that occur in the 30 days following the last dose of protocol therapy must be reported. After that time, only SAEs that are related to protocol therapy are required to be reported. For every SAE which occurs, affiliates must send an SAE report with the following information:

- Safety reporting cover sheet (Procedure Manual appendices)
- Relevant hospital case records and autopsy reports (where applicable)

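### After a first related grade 3–4 AE in Cycle 3 or 4, Section 4.7.4 restarts the supplement and Section 4.9 ends it, and nothing says which rule governs

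*Combined protocol and SAP*

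**What the plan says.** Section 4.7.4 (Dose Modifications) is mandatory and is defined by attribution, not by cycle: "Dose modifications for AEs which are at least possibly treatment-related are must follow Table 1". For an initial grade 3–4 event Table 1 suspends the supplement. The text below it then says: "Return to prior dose after three consecutive days of resolution/baseline grade", with the start of Cycle 3 as the alternative restart point. Only after a failed rechallenge does dosing stop for the rest of the period, and that stop runs to the start of Cycle 3 or the end of Cycle 4. The section also requires full dose at the start of Cycle 3 whatever happened before, and explains: "This is because the agent used during Cycles 1 and 2 differs from that which is used during Cycles 3 and 4".

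Section 4.9 (Discontinuation of Protocol Therapy) says the supplement is given for four cycles, "depending upon chemotherapeutic regimen, or until any of the following occur". One of its eight listed reasons is a "grade 3 or higher AE that is possibly, probably, or definitely related to the genistein/placebo during Cycle 3 or 4". The subject is then off treatment and on follow-up.

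On reporting, Section 9.2.1 requires SAEs in the database within 24 hours, and Section 9.2.3.2 has affiliate sites fax them to the sponsor within 24 hours. For non-serious related events during Cycles 1–4, Table 5 contains the deadline "OnCore: 30 days from end of Cycle" and a 15-day counterpart. Table 6, for follow-up, gives "OnCore: 30 days from end of Reporting Period" for related grade 3 events and 15 days for related grade 4.

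**The concern.** Whether a child on chemotherapy is given the supplement again after a severe event judged related to it is a safety rule, and it should have one answer. Here a clinician who opens the dose-modification section when the event occurs finds a complete, mandatory sequence that ends in re-dosing. A clinician who opens the discontinuation section finds that the child is off treatment. The attribution threshold is low, since a merely possible relationship triggers both rules.

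The choice also decides whether the child stays in treatment-phase assessments or moves to follow-up, where no ANC is scheduled. Sites could therefore handle the same event differently, both in dosing and in what is measured.

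**Working it through.** The plan gives no figure for this point, so the check is a trace of the two rules followed by a bound on the difference.

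**Which events conflict** (all at least possibly related)

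| Event | 4.7.4 | 4.9 | Dosing conflict? |
|---|---|---|---|
| Grade 2, any cycle | Half dose, then return | Not triggered | No |
| First grade 3–4, Cycles 1–2 | Suspend, then return | Not triggered | No |
| First grade 3–4, Cycles 3–4 | Suspend, then return after three clear days | Therapy ends | **Yes** |
| Grade 3–4 after rechallenge, Cycles 3–4 | Stop to end of Cycle 4 | Therapy ends | No |

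Both rules stop dosing at once; they differ only on restarting.

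**Does 4.7.4 reach Cycles 3–4?** The return sentence mentions the start of Cycle 3, which might suggest it concerns Cycles 1–2 only. The next sentence and Table 2 run to the end of Cycle 4, so the section does cover modification and rechallenge in the second period.

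**Is precedence stated?** No. Section 4.7.4 refers to Section 9 but not to 4.9, and 4.9 does not refer to 4.7.4. Sections 4.6 and 4.8.1 do point to 4.9.

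**Doses that 4.7.4 allows and 4.9 does not.** Days are counted from Cycle 3 Day 1. With cycles on schedule, Cycles 3–4 last 42 days (2 × 21) or 28 days (2 × 14). Doses left = last day − restart day + 1.

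- Upper bound: onset Day 1, clear on Days 2–4, restart Day 5. 42 − 5 + 1 = 38, or 28 − 5 + 1 = 24.
- Lower bound: fewer than three clear days before Cycle 4 ends, so 0.
- Assumed example, onset Day 5:
  - clear from Day 8, restart Day 11: 42 − 11 + 1 = 32, or 28 − 11 + 1 = 18;
  - clear from Day 12, restart Day 15: 42 − 15 + 1 = 28, or 28 − 15 + 1 = 14.

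Add 1 to each non-zero count if the last day of Cycle 4 is taken as Day 1 of the next cycle (Table 3, footnote 6). A chemotherapy delay would lengthen the period, because Section 4.7.3 continues the supplement through it.

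**Latest OnCore entry for a non-serious, non-target related event in Cycle 3**

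- 30 days after the end of the cycle: 21 + 30 = Day 51, or 14 + 30 = Day 44.
- 15 days after the end of the cycle: 21 + 15 = Day 36, or 14 + 15 = Day 29.

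Table 5's layout is broken in the text available, so the assignment of 30 days to grade 3 and 15 to grade 4 is taken from Table 6. Under either deadline the entry date falls after the earliest restart on Day 5. Under the 30-day deadline it also falls after the planned end of Cycle 4 (Day 42 or Day 28).

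**The case against.** The strongest reply is that the documents nearly settle the matter. Section 4.9 is the narrower and more cautious rule, its lead-in makes every listed event a terminating condition, and a dose-modification table can apply only to someone still on therapy. The stated change of agent at Cycle 3 fits a deliberate limit: Cycles 1–2 allow a fresh start on the other agent, and Cycles 3–4 do not. The two sections can be read together, with suspension as the immediate action and discontinuation following. The words about the end of Cycle 4 are needed for grade 2 events anyway, so they do not prove an intention to re-dose after grade 3–4.

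That supports 4.9 as the intended rule. It does not repair 4.7.4, whose return step as written covers the case that 4.9 excludes.

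A second reply is that the stop depends on the site's own grading and attribution, not on OnCore, and that other safeguards exist: 24-hour SAE reporting, monthly DSMC review, review of individual AEs by the treating physician or principal investigator, and the Study Chair's continuous monitoring. This stands in part. For serious events the coordinating centre would normally know before a restart. For non-serious events the OnCore dates do not cause the re-dosing; they show only that central notice is not required in time to prevent it. The person reviewing at the site may be the one following 4.7.4.

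It is also fair that 38 doses is an extreme bound, that no event rate is available, and that the Procedure Manual, which was not supplied, may resolve the point.

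**Conclusion.** The contradiction is real but narrow: a first grade 3–4 event, at least possibly related, in Cycle 3 or 4. Section 4.9 is the sensible controlling rule, but the protocol does not say so, and 4.7.4 as written directs the opposite. The excess is 0 to 38 doses per affected child with 21-day cycles or 0 to 24 with 14-day cycles, assuming cycles on schedule; how many children would be affected cannot be estimated from the documents. The unprotected part is mainly non-serious events, because serious ones have a 24-hour route.

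The type I error rate, the stated power and co-primary endpoint (a), which uses Cycles 1 and 2, are not touched. This should be fixed because it is a stopping rule in a multi-site paediatric trial. Confidence is high on the text; whether sites would in fact diverge is not known.

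**What to change.** In Section 4.7.4, limit the return and rechallenge step for grade 3–4 events to Cycles 1–2 and add: *A related grade 3 or higher AE in Cycle 3 or 4 is handled under Section 4.9.* Leave 4.9 unchanged. The cost is one limiting phrase and one cross-reference, with no added patients, visits or blood draws. If the Procedure Manual repeats the rule, align it.

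A separate, inexpensive improvement concerns all eight discontinuation reasons in 4.9 and is not caused by this contradiction. Follow-up under Section 6.4 schedules no ANC. Co-primary endpoint (b) would therefore be missing for subjects who stop the supplement early, or only partly recoverable from the dates of reported grade 4 neutropenia. Cycles whose nadir is 500 cells/µl or more produce no grade 4 event, and Section 7.1 defines their recovery day from the ANC series itself. Add one sentence to 4.9 or 6.4: unless consent is withdrawn, record ANC values already drawn in routine care through the end of chemotherapy Cycle 4, and flag subjects whose chemotherapy was changed. This costs some data entry, and the recovery days would be coarser than under the mandated twice-weekly sampling.
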